**5.8.3.2 Handling of Specimen(s)**

Biopsy samples will be placed in formalin and shipped to the CIML. Blood collection tubes will be shipped on day of blood draw for overnight delivery to the CIML.

**5.8.3.3 Shipping of Specimen(s)**

For archival samples, clinical sites will arrange for the formalin-fixed, paraffin-embedded tumor blocks (preferred) or FFPE slides (if blocks are unavailable) to be shipped at ambient temperature to the CIML. For biopsies done as part of this protocol, tissue in formalin will be shipped overnight at ambient temperature to the CIML. Clinical sites will utilize a web-based specimen system (BSI-Engage) to communicate with the CIML.

**5.8.3.4 Site(s) Performing Correlative Study**

These analyses will be performed in the CIML at the Fred Hutch or an agreed upon vendor or collaborator.

**5.8.4 Whole Blood Immunophenotyping – Exploratory Laboratory Correlative Study #4**

**5.8.4.1 Collection of Specimen(s)**

Blood draws will be performed by venipuncture on study subjects just before, during, and at end of treatment.

**5.8.4.2 Handling of Specimen(s)**

Blood collection tubes (for subsequent PBMC and plasma isolation) will be shipped on day of blood draw for overnight delivery to the CIML.

**5.8.4.3 Shipping of Specimen(s)**

Blood collection tubes will be shipped overnight at ambient temperature to the CIML using CIML established SOPs. Clinical sites will utilize a web-based specimen system (BSI-Engage) to communicate with the CIML.

**5.8.4.4 Site(s) Performing Correlative Study**

These analyses will be performed in the CIML at the Fred Hutch.

**5.8.5 KSHV Humoral Response – Exploratory Laboratory Correlative Study #5**

**5.8.5.1 *Collection of Specimen(s)***

Blood draws will be performed by venipuncture on study subjects. The collection will take place before NT-I7 injection when scheduled on the same day as NT-I7 administration.

**5.8.5.2 *Handling of Specimen(s)***

Blood collection tubes (for subsequent PBMC and plasma isolation) will be shipped on day of blood draw for overnight delivery to the CIML.

**5.8.5.3 *Shipping of Specimen(s)***

Blood collection tubes will be shipped overnight at ambient temperature to the CIML using CIML established SOPs. Clinical sites will utilize a web-based specimen system (BSI-Engage) to communicate with the CIML. The CIML will coordinate shipments of serum, as needed.

**5.8.5.4 *Site(s) Performing Correlative Study***

Batched samples will be analyzed at the Frederick National Laboratory for Cancer Research at the end of the study.

**5.9 Special Studies**

**5.9.1 Immunogenicity Testing**

The formation of anti-drug antibodies and neutralizing anti-drug antibodies to NT-I7 will be evaluated before the first dose of NT-I7, and then again on time points described in Table 3.

**5.9.1.1 *Collection of Specimen(s)***

Blood draws will be performed by venipuncture on study subjects before, during and at end of treatment.

**5.9.1.2 *Handling of Specimen(s)***

Sera will be isolated by the local laboratory and frozen at -80C.

**5.9.1.3 *Shipping of Specimen(s)***

Serum samples will be batch shipped overnight on dry ice to the CIML (Seattle, WA). Sites will utilize a web-based specimen system (BSI-Engage) to communicate with the CIML. The CIML will coordinate the shipment of samples to the agreed upon collaborator or vendor.

**5.9.1.4 *Site(s) Performing Immunogenicity Testing***

Samples will be analyzed at BioAgilytix.

### 5.9.2 NT-I7 Pharmacokinetics

The pharmacokinetic profile of NT-I7 will be assessed to determine if any NT-I7 levels are affected by any ADA that may be observed. The samples will be collected before the first dose of NT-I7 and then again time points described in Table 3. Two PK blood draws for the time points (week 0, week 9, week 18, and week 27) should be performed as follows: 1) a 7 ml draw prior to NT-I7 administration; and 2) a 7 ml draw 3 hr (+/-15min) post NT-I7 administration. Only one PK blood draw is to be performed at week 1 and EOT.

#### 5.9.2.1 *Collection of Specimen(s)*

Blood draws will be performed by venipuncture on study subjects before and during study treatment.

#### 5.9.2.2 *Handling of Specimen(s)*

Sera will be isolated by the local laboratory and frozen at -80C.

#### 5.9.2.3 *Shipping of Specimen(s)*

Serum samples will be batch shipped overnight on dry ice to the CIML (Seattle, WA). Sites will utilize a web-based specimen system (BSI-Engage) to communicate with the CIML. The CIML will coordinate the shipment of samples to the agreed upon collaborator or vendor.

#### 5.9.2.4 *Site(s) Performing Pharmacokinetics Testing*

PK of NT-I7 will be performed by BioAgilytix.

### 5.9.3 Cytokines, including IL-7

Cytokine levels, including endogenous IL-7, will be evaluated before the first dose of NT-I7, and then again on time points described in Table 3.

#### 5.9.3.1 *Collection of Specimen(s)*

Blood draws will be performed by venipuncture on study subjects. The collection will take place before NT-I7 injection when scheduled on the same day as NT-I7 administration.

#### 5.9.3.2 *Handling of Specimen(s)*

Blood collection tubes (for subsequent PBMC and plasma isolation) will be shipped on day of blood draw for overnight delivery to the CIML.

#### 5.9.3.3 *Shipping of Specimen(s)*

Blood collection tubes will be shipped overnight at ambient temperature to the CIML using CIML established SOPs. Clinical sites will utilize a web-based specimen system (BSI-Engage) to communicate with the CIML. The CIML will coordinate shipments of serum to the Fred Hutch Shared Resources lab, or vendor, as needed.

#### 5.9.3.4 *Site(s) Performing Pharmacodynamic Testing*

[figure not shown]
Cytokine assays will be performed at the Fred Hutch Shared Resources or by agreed

upon vendor.

## 6. TREATMENT PLAN

Based on the pharmacodynamic data obtained from the GX-I7-CA-003 study (Q3W) dosing and preliminary data from other ongoing studies with less frequent dosing schedules, NT-I7 can be given less frequently than every three weeks and more frequently than every twelve weeks (e.g., Q9W), and will still lead to similar changes in the ALC and other peripheral blood T-cell subsets.

This is a Phase I, open-label, multicenter study to determine the safety and efficacy of NT-I7 in HIV-negative and HIV-positive patients with KS. A traditional 3+3 design (Figure 6) will be used, with DLT window being the first 28 days of study treatment. Three dose levels of NT-I7 will be administered, 480  $\mu$ g/kg, 960  $\mu$ g/kg and 1200  $\mu$ g/kg injected on Day 1  $\pm$  2 days of every cycle (every 9 weeks).

**Figure 6: 3+3 Phase 1 study design schema.**

All participants enrolled into this study will receive NT-I7 IM injections at the scheduled dose level (Table 8). Participants will be treated at a given dose level every 9 weeks for up to 27 weeks (4 doses) and followed for an additional 12 months. NT-I7 will be held if the ALC is greater than 10,000 cells/ $\mu$ L at the time of administration. There will be no intra-participant dose escalation.

Three participants will be enrolled at dose level 1. If 0 of 3 have a DLT (described in [Section 6.2](#)), dosing will escalate to the next dose level. If 1 of 3 have a DLT, that dose level will expand

to 6 participants. If 1 of 6 participants has a DLT, dosing will escalate to the next highest level. If 0-1 participant has a DLT at dose level 3, an additional 3 participants will be treated at that level.

If two participants have a DLT at dose level 1 or dose level -1, dosing will de-escalate to the next lowest level. Dose levels -1 (360  $\mu\text{g}/\text{kg}$ ) and -2 (240  $\mu\text{g}/\text{kg}$ ) have been defined if there is unexpected toxicity at dose level 1.

The recommended phase 2 dose (RP2D) will be selected according to the following logic, taking into account the MTD determination from the Dose Escalation Phase (Phase I) and the Maximum Effective Dose (MED) level which is defined as the dose level at which maximum effects on peripheral blood T-cell levels and intratumor T-cell levels are observed. The intratumor T-cell levels will dominate if the peripheral blood and intratumor T-cell levels differ. The available data will be assessed by the Protocol PI(s), the Protocol Chair, and the CITN Central Operating and Statistical Center (COSC) to select the RP2D.

- If the MTD is determined AND
  - MTD = MED, then the RP2D = MTD = MED
  - MTD > MED, then the RP2D = MED
- If the MTD is not reached, then the RP2D = MED

Treatment emergent adverse events will be tabulated according to grade and attribution ( $\geq$  possibly attributed to NT-I7 versus  $\leq$  unlikely related to NT-I7).

Response to therapy will be evaluated by clinical exam using AIDS Clinical Trials Group Criteria ACTG criteria at baseline, 9 weeks, 13 weeks, 18 weeks, 27 weeks, and 36 weeks as outlined in the Trial Schema.

**Table 8. NT-I7 Dose Escalation and De-Escalation Scheme.**

Dose Level	NT-I7 Intramuscular (IM)	Route of Administration
DOSE LEVEL minus 2:	240 $\mu\text{g}/\text{kg}$	IM
DOSE LEVEL minus 1:	360 $\mu\text{g}/\text{kg}$	IM
DOSE LEVEL 1:	480 $\mu\text{g}/\text{kg}$	IM
DOSE LEVEL 2:	960 $\mu\text{g}/\text{kg}$	IM
DOSE LEVEL 3:	1200 $\mu\text{g}/\text{kg}$	IM

Abbreviation: IM=intramuscular

## 6.1 Agent Administration

Treatment will be administered on an outpatient basis. Reported adverse events and potential risks are described in [Section 10](#). Appropriate dose modifications are described in Table 8 and [Section 7](#). No investigational or commercial agents or therapies other than those described below may be administered with the intent to treat the patient's malignancy.

### 6.1.1 NT-I7

Subjects will receive NT-I7 IM injections on day 1 ( $\pm$  2 days) of each cycle according to the dose escalation schedule described in Table 8. For information on the injection sites, please refer to [Appendix B](#).

An adjusted body weight will be used to calculate the dose of NT-I7 for patients with a Body Mass Index (BMI)  $>30$  kg/m^2. Please refer to [Appendix B](#) for details on the adjusted body weight calculation. Weight must be collected at baseline and re-assessed prior to each NT-I7 dosing. If the patient's weight has changed  $\pm$  10% from the baseline measurement collected during screening, NT-I7 dose should be re-calculated based on the new weight.

Patients receiving NT-I7 will have their vital signs (heart rate, respiratory rate, blood pressure, and temperature) assessed within 60 minutes before the receiving the NT-I7 injection and will remain under observation for 4 hours after the first injection of NT-I7. Vital signs will be monitored every 2 hours during the post-injection observation period. Patients must be observed in clinic for at least 2 hours following subsequent administration of NT-I7 (Cycles 2, 3 and 4).

Patients will be informed about the possibility of the development of an allergic reaction to NT-I7 (hives, bronchospasm, rash, etc.) and instructed to contact their study physician if they develop such symptoms.

**Table 9: Study Treatment Details**

Regimen Description					
Agent	Premedication; Precautions	Dose	Route	Schedule	Cycle
rhIL-7-hyFc (NT-I7)	antihistamines or antipyretics/analgesics can be given prior to NT- I7 dosing a	Dose in µg/kg b	IM	Day 1 of each cycle	63 days

Abbreviations: IM=intramuscular.

aNot permitted for the first dose. Optional for subsequent injections.

bRefer to Table 8 for assigned dose level.

### 6.1.2 Other Procedures: Biopsy (core needle, punch or excisional)

Biopsy/tumor tissue will be obtained by punch biopsy, incisional or excisional biopsy. Core needle biopsy or excisional biopsy may be acceptable for visceral lesions depending on clinical circumstance.

**Note:** Baseline tumor biopsy (fresh) may be obtained up to 28 days prior to treatment initiation.

An archival tumor sample obtained within 1 year of screening is allowed if the pre-treatment biopsy is deemed unsafe or technically not feasible.

Tissue based studies will be performed on mandatory biopsies collected at baseline and at 9 weeks, with an optional biopsy at 13 weeks. Biopsy scheduled for collection at 9 weeks will be obtained prior to dosing on Cycle 2, Week 9, Day 1 or at the End of Treatment visit, whichever occurs first. Effect on tumor microenvironment will be assessed by multi-spectral IHC on serial biopsies.

## 6.2 Definition of Dose-Limiting Toxicity

Dose-limiting toxicity is defined as any AE occurring within the first 28 days (i.e., Cycle 1, Day 1 through Week 4 Day 7) that is considered to be at least possibly, probably, or definitely related to the protocol treatment (NT-I7) per the investigator, and that meets at least one of the non-hematologic or hematologic criteria below.

All toxicities will be graded using NCI Common Terminology Criteria for Adverse Events (CTCAE) Version 5.0 or current version.

### 6.2.1 DLT Criteria

1. Grade  $\geq 3$  non-hematologic AE (not laboratory), with following exceptions:
  - a. Grade  $\geq 3$  diarrhea, nausea, or vomiting that resolves within 2 days with use of anti-emetics or antidiarrheals per standard of care.
  - b. Grade 3 fatigue lasting  $\leq 3$  days.
2. Grade 4 neutropenia lasting  $\geq 5$  days.
3. Febrile neutropenia Grade 3 or Grade 4:
  - Grade 3 is defined as absolute neutrophil count (ANC)  $< 1000/\text{mm}^3$  with a single temperature of  $> 38.3$  degrees C (101 degrees F) or a sustained temperature of  $\geq 38$  degrees C (100.4 degrees F) for more than 1 hour.
  - Grade 4 is defined as ANC  $< 1000/\text{mm}^3$  with a single temperature of  $> 38.3$  degrees C (101 degrees F) or a sustained temperature of  $\geq 38$  degrees C (100.4 degrees F) for more than 1 hour, with life-threatening consequences and urgent intervention indicated.
4. Other Grade 4 hematologic toxicity lasting  $\geq 7$  days, except thrombocytopenia:
  - Grade 4 thrombocytopenia of any duration.
  - Grade 3 thrombocytopenia associated with clinically significant bleeding.
- Note:** Peripheral lymphocytopenia after the first NT-I7 injection is not a sign of toxicity; it reflects the lymphocytes “homing effect” of NT-I7. Lymphocyte counts usually come back to baseline 5 to 7 days after the first injection.
5. Any Grade 3 or Grade 4 non-hematologic laboratory value if:
  - Clinically significant medical intervention is required to treat the subject, or
  - AIDS defining opportunistic infection that occurs in the setting of new persistent

- elevation of HIV viral load >400 copies/mL over 90 days despite adherence to ARV
- The abnormality leads to hospitalization.

6. Other Grade  $\geq 3$  clinical laboratory abnormalities must be reversible to  $\leq$  Grade 1 within 72 hours with outpatient care and/or monitoring AND must not be considered clinically significant by the treating physician to be excluded from the definition of DLT.
7. Any treatment-related toxicity that causes the subject to discontinue treatment during Cycle 1.
8. Grade 5 toxicity.

Once all subjects in a cohort have completed the 4-week (28 days) DLT window, the AEs will be assessed by the Protocol PI(s), the Protocol Chair, and the CITN Central Operating and Statistical Center (COSC).

The subjects must complete the full 4-week DLT window to be considered evaluable for DLTs. Subjects who discontinue from the study before completion of the full 4-week DLT window for reasons other than the occurrence of a DLT (e.g., withdrawal of consent, rapid tumor progression, death due to rapid tumor progression, AE that does not meet DLT criteria) will not be considered evaluable for DLTs and will be replaced.

All subjects will be monitored for occurrence of DLT. Monitoring of all safety and toxicity data is done by the protocol PI and CITN COSC on a real-time basis as data are entered into Medidata Rave using the Web Reporting Module. All participating sites must notify the protocol PI and CITN COSC when a DLT has occurred.

### **6.3 General Concomitant Medication and Supportive Care Guidelines**

Because there is a potential for interaction of NT-I7 with other concomitantly administered drugs, the case report form must capture the concurrent use of all other drugs, over-the-counter medications, or alternative therapies. The PI should be alerted if the patient is taking any agent known to affect or with the potential for drug interactions. The study team should check a frequently-updated medical reference for a list of drugs to avoid or minimize use of.

#### **6.3.1 General Concomitant Medication and Supportive Care Guidelines**

Concomitant therapy includes any prescription medications or over-the-counter preparations used by a patient between the 7 days preceding the baseline evaluation and up to 30 days after the last dose of study treatment. Concomitant medications administered 30 days after the last dose of study treatment should be recorded for SAEs and events of special interest or clinical interest (ECIs) as defined in [Section 10](#).

Subjects may receive medications that the investigator deems to be medically necessary, with the specific exception of non-protocol specified chemotherapy, radiotherapy, anti-neoplastic biological therapy or other investigational agents. Subjects who require the use of any of the aforementioned treatments for clinical management should be removed from the study during

that period. Standard antibiotic therapy will always be allowed.

Patients who experience hypersensitivity, potential allergic reaction or skin reaction, including injection-associated symptoms, may be treated symptomatically with acetaminophen, ibuprofen, diphenhydramine, and/or cimetidine or another H2 receptor antagonist, as per standard practice. Serious injection-associated events manifested by dyspnea, hypotension, wheezing, bronchospasm, tachycardia, reduced oxygen saturation, or respiratory distress should be managed with systemic corticosteroids, bronchodilators, intravenous fluid, epinephrine, or other supportive therapies as clinically indicated.

Topical corticosteroids to treat injection site reactions are allowed.

### 6.3.2 Excluded Therapies

If there is a clinical indication for using any medication or vaccination specifically prohibited during the study, discontinuation from study treatment or vaccination may be required. The final decision on any supportive therapy or vaccination rests with the investigator and/or the subject's primary physician. However, the decision to continue the subject on study treatment requires the mutual agreement of the investigator, the study sponsor and the subject. This includes but is not limited to the following therapies:

- Antineoplastic systemic chemotherapy or biological therapy
- Immunotherapy not specified in this protocol
- Chemotherapy not specified in the protocol
- Investigational agents other than NT-I7
- Radiation therapy

*Note:* Radiation therapy to a symptomatic solitary lesion or to the brain may be allowed at the investigator's discretion.

- Live vaccines within 30 days prior to the first dose of study treatment and while participating in the study. Examples of live vaccines include, but are not limited to, the following: measles, mumps, rubella, varicella/zoster, yellow fever, rabies, BCG, and typhoid vaccine. Seasonal influenza vaccines for injection are generally killed virus vaccines and are allowed; however, intranasal influenza vaccines (e.g., FluMist®) are live attenuated vaccines and are not allowed. Jynneos Monkeypox Vaccine is not considered a live virus vaccine in terms of eligibility or administration of NT-I7. Even though the Jynneos Monkeypox Vaccine can be considered a live virus because it does infect the cells upon injection, it is 'replication incompetent', so the localized infection caused by the vaccine cannot spread, and therefore poses a very low risk of complications associated with viremia.

- In participants who have not yet started treatment, Jynneos Monkeypox Vaccine should be administered at least 3 days prior to start of treatment when possible.
- In participants who are receiving study therapy, Jynneos Monkeypox Vaccine should not be administered on the same day as IM injection of NT-I7. Where possible, the vaccine should be administered during an off week, or at least a week apart from an injection day. A minimum gap of at least 3 days is strongly recommended, based on CDC guidance that most vaccine-related adverse events occur within 3 days of injection.
- Administration of Jynneos Monkeypox Vaccine should be documented as a concomitant medication.
- Systemic glucocorticoids for any purpose other than to modulate symptoms from an AE that is suspected to have an immunologic etiology. The use of physiologic doses of corticosteroids may be approved after consultation with the Sponsor.

**Note:** Inhaled steroids are allowed for management of asthma.

**Note:** As stated in Section 6.3.1, topical corticosteroids to treat injection site reaction are allowed.

- Immunostimulatory and immunosuppressive agents are prohibited.
- No data exist regarding the interaction of NT-I7 with commonly used herbal or non-traditional medications. Patients should be instructed not to use such medications while receiving NT-I7 therapy or use with caution at the investigator's discretion. Close monitoring is required while the patient receives study treatment. Herbal therapy intended as anticancer therapy must be discontinued  $\geq$  1 week before initiation of study treatment.

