#### 12.1.2.3 Partial Response

No progressive disease (see below and noting, that single lesions which split up into 2 or more smaller lesions during the course of treatment will still be counted as one); no new lesions occurring in previously uninvolved areas of the body; no new visceral sites of involvement or the appearance or worsening of tumor-associated edema or effusions *and*:

- A 50% or greater decrease in the number and/or size of previously existing lesions **lasting for at least 4 weeks or**
- Complete flattening of at least 50% of all previously raised lesions (i.e., 50% of all previously nodular or plaque-like lesions become macular) **lasting for at least 4 weeks or**
- A 50% decrease in radiologically measurable visceral lesions sustained without evidence of re-growth **for at least 4 weeks or**
- A 50% decrease in radiologically measurable visceral lesions sustained without evidence of re-growth **for at least 4 weeks or**
- Subjects who otherwise meet the criteria for a CR but still have residual tumor-associated edema or effusions will be classified as having a PR.

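### The response rules have no exception for a lesion irradiated on study, so its regression can contribute to a partial response credited to NT-I7, and the passages on whether such radiation is allowed need reconciling

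*Combined protocol and SAP*

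**What the plan says.** **Whether radiation may be given on study.** Section 6.3.1 permits medically necessary medication "with the specific exception of non-protocol specified chemotherapy, radiotherapy, anti-neoplastic biological therapy or other investigational agents". It continues: "Subjects who require the use of any of the aforementioned treatments for clinical management should be removed from the study", for as long as that need lasts. Section 6.3.2 lists radiation among the excluded therapies, but its note says: "Radiation therapy to a symptomatic solitary lesion or to the brain may be allowed", leaving the decision to the investigator. The opening of 6.3.2 says that "the decision to continue the subject on study treatment requires the mutual agreement of the investigator, the study sponsor and the subject". Section 6.1 has a general bar: "No investigational or commercial agents or therapies other than those described below may be administered with the intent to treat" the malignancy. Section 6.6 and Study Calendar note b place the end-of-treatment visit just before any other cancer therapy begins. Note d puts participants who start new anticancer treatment on survival follow-up only. None of these says whether radiation allowed under the 6.3.2 note counts as such treatment.

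**How response is scored.** One route to PR in Section 12.1.2.3 is "A 50% or greater decrease in the number and/or size of previously existing lesions", held for at least 4 weeks. The others are flattening of at least half the raised lesions, a 50% fall in measurable visceral disease, or meeting CR criteria apart from residual edema or effusion. Section 12.1.1.1 asks that marker lesions be ones that have never had local therapy such as radiation. Appendix D (follow-up examination in Section 1, and Section 3) has the same marker lesions and the same areas followed from entry onward. With more than 50 lesions at entry, only representative areas are used for responses short of CR.

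**How response is analyzed.** Section 9.4.1 takes the best response within 12 months of the first dose. Section 9.4.2 gives no censoring rule for radiation.

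**The concern.** The never-irradiated condition shows that the sponsor recognized local therapy as a confounder of response, but it is written for choosing marker lesions. Once chosen, the lesions are followed, and no rule in Section 9.4, Section 12.1 or Appendix D says what to do if one is irradiated later. The same silence applies to lesions that enter only through the total count or the raised-lesion count.

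If a site uses the 6.3.2 allowance and keeps assessing response, shrinkage caused by radiation enters the same sums as shrinkage under NT-I7. The trial has a single arm, so no comparison group would reveal it. Lesions irradiated for symptoms may also be among the largest. And because the passages on permission differ, two sites could handle the same event differently: one stopping response follow-up, the other continuing to score.

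**Working it through.** **1. Reproduce the protocol's example (Appendix D, Section 1.1 A).** Area is the product of the two perpendicular diameters:

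- 35×16 = 560; 25×25 = 625; 57×39 = 2223; 32×22 = 704; 47×16 = 752 mm²
- Sum = 4864 mm², matching the stated total
- PR threshold = 0.5 × 4864 = 2432 mm²

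**2. Clear the largest lesion completely.**

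- Its share: 2223 / 4864 = 45.7%
- Area left: 4864 − 2223 = 2641 mm², above 2432, so this alone is not PR
- Further shrinkage needed from the other four: (2641 − 2432) / 2641 = 209 / 2641 = 7.9%, against 50% across all lesions without radiation

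**3. Clear it only in part.**

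- 75% shrinkage removes 0.75 × 2223 = 1667.25 mm². The other four must lose (2432 − 1667.25) / 2641 = 29.0%.
- 50% shrinkage removes 1111.5 mm². The other four must lose (2432 − 1111.5) / 2641 = 50.0%, so the irradiated lesion then gives no advantage.

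**4. When one lesion gives PR alone.** A lesion with share s of a baseline total, shrinking by fraction f, reaches the threshold only if s × f ≥ 0.50.

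- Marker area: s must be at least 50%. A 60% share needs 0.50/0.60 = 83.3% shrinkage, an 80% share needs 62.5%, and a sole marker lesion needs 50%. Appendix D allows fewer than five marker lesions.
- Lesion count or raised-lesion count: one of n lesions gives a fall of 1/n. That is 50% at n=2, 33.3% at n=3, 10% at n=10 and 2.0% at n=49, so PR alone requires n ≤ 2. For the total count the lesion must disappear, because flat lesions are still counted.
- Visceral disease: the lesion must dominate the measurable visceral total.

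**5. Effect on ORR.** One responder is worth 1/n.

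- n = 20 (maximum enrollment, Section 9.2): 1/20 = 5.0 points. Reclassifying a single responder takes ORR from 5.0% (exact 95% CI 0.1 to 24.9) to 0% (0 to 16.8).
- n = 6 (smallest subset analyzed, Section 9.4.1): 1/6 = 16.7 points, from 16.7% (0.4 to 64.1) to 0% (0 to 45.9).

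**The case against.** There is a fair case that little is wrong.

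- **The passages may be compatible.** Section 6.3.1 excludes radiotherapy that is not protocol-specified, and the 6.3.2 note could be the named exception. A reader might instead infer a flat contradiction. The documents do not establish either reading: 6.3.1 makes no reference to the note, and the note does not lift the removal rule.
- **Follow-up may stop first.** If radiation to a KS lesion is new anticancer treatment, note d ends response assessment before a PR could arise. That would remove the problem, but the text does not say that radiation allowed under 6.3.2 is such treatment. Section 6.4 names progression requiring systemic therapy as a reason to stop, which local radiation does not meet in itself.
- **The marker rule may reach further.** Section 12.1.1.1 can be read literally as selecting marker lesions again when response changes, so the never-irradiated condition would apply then too. Appendix D points the other way, since the same lesions are followed throughout, and the condition does not cover lesion counts or flattening on any reading.
- **PR is hard to reach.** It must last 4 weeks with no progression criterion met, and a lesion irradiated because it grew may already have contributed to progression. This stands and limits frequency.
- **ORR carries little weight here.** It is secondary and described as preliminary, with a more precise estimate left to a later expansion cohort. This stands and limits importance.

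**Conclusion.** The point holds as a minor one. The passages on permission must be reconciled. Where radiation is allowed and response follow-up continues, the rules as written let the irradiated lesion's regression contribute to a PR attributed to NT-I7.

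A reader might infer two stronger things that the documents do not support. First, that every lesion counts: marker area uses selected lesions, and above 50 lesions at entry only representative areas enter PR. Second, that one irradiated lesion would generally create a PR by itself: it does so only if it is one of at most two counted or raised lesions, holds at least half the marker area, or dominates measurable visceral disease. In the protocol's own example it falls short, leaving 2641 mm² against 2432 mm².

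The size is 5.0 points of ORR per misattributed responder at n=20 and 16.7 at n=6; such a participant would also enter the duration-of-response analysis. The 7.9% figure assumes complete clearance of the largest lesion in an illustrative example that is not trial data. How often radiation would be used is not given and is probably low. The DLT-based primary endpoint is unaffected.

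**What to change.** 1. Reconcile Section 6.3.1, the note and opening of Section 6.3.2, and Study Calendar note d. State whether radiation to a symptomatic solitary lesion is allowed on study, who agrees to it, and whether response follow-up then continues. Which clinical rule applies is for the sponsor to decide.

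2. If response follow-up can continue, add to Section 12.1 and Appendix D that shrinkage, flattening or disappearance of a lesion after on-study local radiation does not count toward CR or PR. One way is to hold the lesion at its pre-radiation size and character for response. Its later growth should still count toward progression, so keep measuring it and state the reference value. Freezing it for every calculation would hide regrowth.

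3. Flag these participants and, in Section 9.4, report ORR and PFS with and without them.

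The cost is a few sentences and one data flag, with no change to sample size or visits. The downside is that an irradiated participant may be unable to reach CR, so ORR may be slightly less favorable. Setting the rule in advance avoids deciding a responder's status after seeing the result.
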